### 8.3 ADVERSE EVENT REPORTING REQUIREMENTS

Adverse events should be reported to Procyrion on the Adverse Event Electronic Case Report Form (AE eCRF) and using one eCRF per AE.

The Investigator must report SADEs and SAEs to Procyrion as soon as possible, but in no circumstances later than 24 working hours after the Investigator first learns of the event, at the following email address:

*By email to: [[contact]](mailto:[contact])*

The initial report must be followed by as much information is available and ideally should include complete documentation, including the time and date of onset, description of the event, severity, duration, actions taken and outcome (if known).

All AEs (regardless of severity or relationship to the study device) will be recorded on the eCRF.

Table 1: Timeline for Reporting of Adverse Events

Type	Report to	Reporting Timeframe (from time of learning of event)
Device Deficiency	Sponsor	Within 2 working days
AE / ADE	Sponsor	Within 2 working days
	EC/IRB	Per EC/IRB reporting requirements
SAE / SADE / USADE / UADE	Sponsor	Within 1 working day
	EC/IRB	Per EC/IRB reporting requirements

## 9 STATISTICAL CONSIDERATIONS

---

For the primary purposes of this pilot study, each patient’s data will be reviewed individually. The sample size of up to 20 implanted patients is based upon industry standards for early-stage studies of medical devices; the sample size is not statistically derived or powered to show any significant effect. This study is not designed to provide statistically significant outcomes. The study will provide data to be used for subsequent trial design and possible further development of the Aortix System.

## 10 ETHICAL, REGULATORY, AND ADMINISTRATIVE CONSIDERATIONS

---

### 10.1 INFORMED CONSENT

A patient informed consent form (PICF) template will be provided. If necessary, updates to the template can be made while leaving in the required elements of the PICF. Prior to submission to the IRB/IEC, the investigator customized template must be reviewed and approved by the Sponsor. It is the investigator’s responsibility to obtain IRB/EC approval of the updated version of the PICF prior to enrolling any patients into the study.

The Investigator must ensure that each study patient provides written informed consent for their inclusion in the study after explaining the rationale for and the details, aims, and objectives of the study, the risks and benefits of participation, alternative treatments, and the extent of the patient’s involvement. Patients will also be informed that their participation in the study is voluntary and that they may refuse to participate or withdraw from the study at any time.

Each study patient must sign and date the informed consent, and the person obtaining consent must sign and date the consent confirming that he/she fully explained the study to the patient

and the consent process must be documented accordingly. The Investigator must ensure that no patient is subject to any non-standard, study-required procedures before the patient has given his/her written informed consent.

After obtaining signature of the patient, duly signed informed consent forms, as well as written information given to patients, shall be kept and archived in the Investigator file according to the requirements of the country's regulations and site's requirements.

In circumstances where there is new information available that may affect a patient's willingness to continue to take part in the study, this information will be discussed with the patient.

Pediatric, legally incompetent, or other vulnerable patients are not eligible for the study.

## 10.2 INVESTIGATOR RESPONSIBILITIES

The investigator is responsible for clinical use of the Aortix System at the study site. The Investigator will assume overall responsibility and accountability for the research team and for the clinical data obtained from patients participating in the study. The Investigator will be responsible for:

- Ensuring EC/IRB approval for this Investigational Plan and any amendments are obtained prior to commencement.
- Ensuring that the clinical study is conducted according to this Investigational Plan, federal, state, and local regulations, ICH Good Clinical Practices, applicable standards and the signed Investigator Agreement.
- Obtaining informed consent on the approved EC/IRB informed consent form prior to any study participation.
- Collecting all data as required per the protocol and maintaining source documentation for data supplied
- Reporting adverse events to the EC/IRB, regulatory agencies, and the Sponsor, as required.
- Controlling any investigational device(s) stored at their site. This includes monitoring and return of devices to Sponsor.
- Protecting the rights, safety, and welfare of the patients.
- Maintaining records and reports.
- Assisting in identification of potential patients for the study.

### 10.2.1 Investigator Records

The investigator will maintain complete, accurate, and current study records during the course of the clinical trial. The Sponsor will notify the Investigator when the records can either be destroyed or forwarded to the Sponsor, in accordance with applicable regulations. The clinical trial records must be maintained by the site until that notice is provided. All records should be made available if requested by relevant authorities. These records include:

- Subject Records: Maintain signed informed consent forms, copies of all completed CRFs and supporting documentation (laboratory reports, vascular scan reports, etc.), and records of exposure of each patient to the device (procedure note for example).

- Investigational Plan: Keep a current copy of the Investigational Plan and any amendments, including the Instructions for Use and the Investigator's Brochure.
- USADE / UADEs: Record of all reports and information pertaining to unanticipated device effects following the required timelines.
- Ethics Committee (EC) / Institutional Review Board (IRB): Maintain all information and correspondence pertaining to EC/IRB review and approval of this clinical study, including a copy of the EC/IRB approval letter and a blank informed consent form approved by the EC/IRB.
- Investigator Agreements: Keep copies of the signed Investigators' Agreements with the Investigators' Curriculum Vitae attached.
- Other: Save any pertinent correspondence and/or records that may be required by applicable laws and regulations

### 10.3 SPONSOR RESPONSIBILITIES

The sponsor of this study, Procyron or its designee, is responsible for the following:

- Selecting and training qualified Investigators
- Providing Investigators and study sites with any new risk information in a timely manner
- Ensuring that site EC/IRB review and approval are obtained prior to any study related procedures and ensuring approvals remain current.
- Registering the trial and submitting applications to the appropriate regulatory authorities, as required.
- Ensuring that national regulatory bodies are duly informed of and allow the clinical trial to commence.
- Ensuring that EC/IRBs and any applicable national regulatory bodies are informed of significant new information about the clinical study.
- Reviewing the investigator's assessments of adverse events and reviewing all device deficiency reports
- Conducting evaluations of adverse events, especially USADE/UADEs and reporting to EC/IRBs and regulatory bodies as required.
- Controlling the device(s) under investigation.
- Maintaining adequate contact with the Investigator and conducting data monitoring to ensure compliance with the Investigational Plan and to ensure the site continues to be adequate for this study.

### 10.4 STUDY MONITORING

Procyron will ensure appropriate sites and investigators are selected. Procyron will conduct a Site Initiation visit with the Investigator and Research Team to review the details of the protocol, study procedures, device instructions, and to confirm all required study documentation is in place prior to enrollment of the first patient. Occasional site visits will be conducted by an authorized Procyron representative throughout the study per the monitoring plan. Procyron will also contact or visit the investigator at the end of the study and arrange for the return shipment of all unused devices and any other study related equipment.

## 10.5 CLINICAL EVENTS COMMITTEE (CEC)

An independent clinical events committee (safety committee) (CEC) will be utilized in this study for adverse event adjudication. All clinical events will be reviewed by the committee. The committee will consist of physicians who are not participating in the clinical study.

The sponsor will ensure that adequate source documentation is gathered prior to bringing an event before a committee. Additionally, the sponsor will remove all identifiers to site and patient. If an event goes to the CEC and the committee requests additional source documentation, the event will be listed as pending and every attempt will be made to bring the event back to the next meeting. Additionally, if upon review of the source documents, the CEC believes there is an adverse event that has not been reported, the CEC has the authority to request additional AE(s) be reported. Reports will show the CEC classification, once final as the final classification. In interim reports, pending events will be listed with the investigator classification. Deaths will be reported separately and the event leading to the death will be shown separately only if designated by the CEC as a separate event. Example, death from cardiac arrest is not reported as both a cardiac arrest and a cardiac arrest death.

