## 3.1 STUDY OBJECTIVES

### 3.1.1 Safety

- 1) Observe the nature, severity, and frequency of adverse events associated with the delivery and use of the Aortix System

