## 3.2 STUDY ENDPOINTS

### 3.2.1 Primary Safety Endpoint

- 1) Rate of Occurrence of Serious Adverse Events related to the Aortix implant, retrieval, and therapy (rate will be calculated and reported) [timeframe: enrollment to 30 days post-surgery]

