### 3.2.3 Other Data to be Characterized and Reported

- 1) Rate of all adverse events, including death over the course of the study
- 2) Characterize AKI stages as defined by the KDIGO criteria observed postoperatively
- 3) Characterize serum Creatinine changes over the course of the study
- 4) Characterize urine output pre- and post-surgery
- 5) All-cause 30-day post discharge readmissions (if discharged by day 30 post-surgery)
- 6) Characterize the rate of patients remaining hospitalized 7, 14, and 30-days post-surgery.
- 7) Characterize the length of stay in the ICU/CCU and total duration of length of stay in the hospital post-surgery

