### 8.1 SUBJECT DEATH

If a patient dies during or after deployment or retrieval of the Aortix Pump and the death is believed to be related to the device or procedure, the Investigator will make every effort to have an autopsy performed to help determine the extent to which the patient's death was related to the device/procedure. The Aortix pump should be returned to Procyron.

All subject deaths which occur in subjects prior to study exit/withdrawal, regardless of causality or study relationship, must be reported to Procyron. Investigator must provide a detailed narrative summary to include as much detail that is known regarding the circumstances surrounding the death. All deaths will be brought to the clinical event committee for adjudication and will be reported using standard mortality classifications.

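### Section 10.5 by default shows a fatal complication only as a death, so a table by event type would omit the fatal cases and understate that complication

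*Protocol*

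**What the plan says.** Section 10.5 of the protocol gives the clinical events committee (CEC) the last word on how events are reported: "Reports will show the CEC classification, once final as the final classification". Deaths are then reported on their own, and "the event leading to the death will be shown separately only if designated by the CEC as a separate event". The example given is that "death from cardiac arrest is not reported as both a cardiac arrest and a cardiac arrest death".

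Section 8.1 adds: "All deaths will be brought to the clinical event committee for adjudication and will be reported using standard mortality classifications". It also requires a detailed narrative for every death.

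The uses of these data are set in Section 3:

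- The safety objective (3.1.1): "Observe the nature, severity, and frequency of adverse events associated with the delivery and use of the Aortix System".
- The primary safety endpoint (3.2.1): "Rate of Occurrence of Serious Adverse Events related to the Aortix implant, retrieval, and therapy (rate will be calculated and reported", from enrollment to 30 days after surgery.
- Among the other data (3.2.3): "Rate of all adverse events, including death over the course of the study".

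Section 7.2 lists aortic injury, bleeding, limb ischemia, embolism and other complications as separate risks alongside death, and says that their likelihood in this population is unknown.

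**The concern.** The rule is there to prevent double counting, which is a proper aim for a total. As worded, though, it reaches further than totals. A complication that kills the patient moves to the death category and leaves its own category, unless the CEC decides otherwise on grounds that the protocol does not state.

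A row for aortic injury or bleeding would then hold only the survivors of that complication plus any fatal case the CEC chose to designate. The frequency would be understated and the severity cut off below death, whereas the objective asks for both. The error runs one way: the rule can remove cases from a row but never add them.

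This bears on later use of the data. Section 9 says that the study will inform the design of subsequent trials. Someone taking a complication rate from a table by event type would take one that may exclude its worst cases, and could not tell whether it does without going back to the deaths.

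**Working it through.** The protocol states no figure that depends on this rule, so there is nothing to reproduce. The check has two parts: what the sections say together, and how much one omitted case weighs.

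**1. The sections side by side**

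- Section 10.5: death-only display is the default, showing the causal event is the exception, and the exception needs a positive act by the CEC. No criterion is attached.
- Section 8.1: deaths are adjudicated and classified. It does not say that the causal event also counts under its own type.
- Section 8.2: an adverse event that led to death is a serious adverse event. A device-related death therefore still counts once in the overall rate of Section 3.2.1.
- Sections 3.1.1 and 3.2.3: neither names a rate for a particular complication. Rates by type are implied by an objective that asks for the nature and frequency of events.

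The effect is thus confined to counts broken down by event type.

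**2. Weight of one case (illustration)**

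Input: n = 20 implanted patients, the upper limit in Section 9. The case counts below are assumptions. Intervals are exact (Clopper-Pearson) 95% limits.

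- One omitted fatal case lowers its row by 1/20 = 5 percentage points.
- Two cases, one fatal: the row shows 1/20 = 5.0% (0.1% to 24.9%) instead of 2/20 = 10.0% (1.2% to 31.7%).
- One case, fatal: the row shows 0/20 = 0% (0% to 16.8%) instead of 1/20 = 5.0% (0.1% to 24.9%).

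**3. Range over assumed rates**

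Let p be the true complication rate and f the share of cases that are fatal. The documents give neither. Suppose the CEC designates no causal event as separate. Then

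- expected rate shown = p × (1 − f);
- chance that at least one of 20 patients has a case missing from the row = 1 − (1 − p × f)^20.

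| p | f | Rate shown | Chance of at least one omission |
|---|---|---|---|
| 5% | 10% | 4.5% | 9.5% |
| 5% | 50% | 2.5% | 39.7% |
| 10% | 25% | 7.5% | 39.7% |
| 15% | 10% | 13.5% | 26.1% |
| 15% | 50% | 7.5% | 79.0% |

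For example, with p = 15% and f = 50%: 0.15 × 0.5 = 0.075 shown, and 1 − 0.925^20 = 0.790.

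**The case against.** The strongest reply is that no named endpoint is harmed. The primary safety endpoint is one overall rate, the item in Section 3.2.3 is a rate over all adverse events, and a fatal related complication stays in both as a death. This stands. A reader might infer from Section 10.5 that the primary safety rate is understated; Section 8.2 rules that out, because a related death is itself serious.

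Second, the cause is not lost. The label in the protocol's own example joins the cause to the death, every death needs a narrative and adjudication, Section 8.3 asks for one form per adverse event, and Section 9 makes individual patient review the main approach. This also stands. A reader might infer that fatal complications disappear from the report; the documents do not support that. The cause can be recovered, but the reader of a table by event type has to recover it.

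Third, the CEC consists of independent physicians and may designate the causal event. The only example is cardiac arrest, where event and death nearly coincide; an aortic injury that later proves fatal is a case the committee might well show separately. That softens the rule, but without a criterion it remains unsettled which fatal cases appear in their rows.

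Fourth, table layout is usually left to the statistical analysis plan, which is not at hand. That would answer a complaint about missing detail. Here the protocol itself fixes a reporting rule, and an analysis plan that followed it would carry the omission over.

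Fifth, the figures are hypothetical and the intervals overlap widely. Agreed: they show the weight of one case among 20 and are not a forecast.

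**Conclusion.** The point holds for tabulations by event type. Under the default in Section 10.5, a fatal case is missing from the row of the complication that caused it unless the CEC designates it, so such a row can only be too low. With 20 implanted patients each omitted case is worth 5 percentage points. How many cases would be omitted cannot be said from the documents; it depends on the complication rate, the fatal share and the CEC's practice, none of which is given.

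The point does not reach the overall rate of related serious adverse events, does not show that information on cause is lost, and does not establish which complications would be most affected, since the documents contain no fatality figures. It is a badly drawn reporting rule that should be corrected, with a modest effect on how the study reads.

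**What to change.** Reword the sentence in Section 10.5 so that the rule against double counting governs totals only:

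- in the overall rate of serious adverse events, each patient counts once;
- in tables by event type, fatal and non-fatal cases count together, with the fatal ones flagged;
- the separate list of deaths names the causal event as adjudicated by the CEC.

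Inclusion of a fatal case in its event row then no longer depends on an undefined designation. No new data are needed, because every death is already adjudicated with a narrative. The cost is the changed wording and one extra column, and some event types will show slightly less favourable rates.

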## 10.6 DATA MANAGEMENT

Procyron or its designee will be responsible for data management. Procyron will use an electronic database, electronic case report forms (eCRF), and electronic signatures. The eCRFs will be provided by Procyron or its designee. All data requested on the eCRF are considered required. Pertinent records in connection with the study, including patient charts, laboratory data, and related information will be made available to the sponsor on request while protecting the confidentiality of patient information. All data requested on the CRF is considered required data unless otherwise specified as "if available." Pertinent records in connection with this study shall be maintained. This would include patients' charts, laboratory data, and any documents used to support data entered onto CRFs. Patient worksheets may be provided to collect data not commonly found in patients' medical records.

The most current version of MedNet Solution's iMedNet EDC will be used for this study. The Principal Investigator, or his/her designee, must e-sign each patient's case book to confirm the accuracy and completeness of all data. Each patient enrolled in the study will be assigned a unique patient identifier. Completed eCRFs will be submitted to Procyron. Manual and automatic data review will be performed to identify discrepancies and queries will be issued manually or created within the EDC system. Site staff will be responsible for resolving all queries in a timely fashion, within the EDC system.

iMedNet is a web-based EDC system for the collection and management of clinical trial data developed and provided by MedNet Solutions. MedNet Solutions is responsible for the creation, validation, and development of 21 Code of Federal Regulations (CFR) Part 11 compliant clinical trial databases. The iMedNet EDC is a secure site that is compliant with the Health Insurance Portability and Accountability Act (HIPAA) regulations for patient privacy. MedNet utilizes Amazon Web Services provided by ClearDATA to host and protect production data. Data is redundantly backed up utilizing automated routines and AWS CLI Scripts. The primary data center is SSAE 16 Type 2 certified and HITRUST certified. MedNet utilizes transport layer security (TLS) encryption on all data transmissions to and from their servers. MedNet Solutions IT staff performs regularly scheduled vulnerability scans against IT resources to ensure compliance with regulatory standards and industry best practices.

## 10.7 PUBLICATION POLICY

Publication and Authorship will be aligned with the International Committee of Medical Journal Editors (ICMJE) recommendations ([www.icmje.org](http://www.icmje.org)). Procyrion will seek to publish, in appropriate peer-reviewed journals and scientific conferences, results of the clinical study. While study results are owned by Procyrion, all data on which a publication is based will be made available to all authors as required for their participation in the publication process. Furthermore, with sponsor permission, data may be published or used by study investigators provided that such publication or use is in accordance with this protocol, the Investigator Agreement, and Procyrion's Publication and Authorship Guidelines.

## APPENDIX A: SCHEDULES OF DATA COLLECTION

Category	Schedule of Data Collection for Patients with Aortix Removed at the Conclusion of Surgery (Aortix Arm)					
	Pre-Surgery Period (Baseline Monitoring)	Surgery and Aortix Implant	Post-Surgery Monitoring (in Hospital)			Study Exit (Day 30 Post-Surgery)
	Current hospitalization once	Once	24 Hours Post-Surgery (± 1 hour)	At 72 hours Post-Surgery (± 4 hours)	Daily starting at 24 Hours Post-Surgery until Hospital Discharge or Day 7, if still hospitalized (± 6 hours)	Study Exit Visit ± 3 Days
Informed Consent	X					
Anatomy Screening	X					
Med History and Physical Exam	X					
Collect Admission H&P	X					
Weight & Ejection Fraction (EF)	X			X*		
Vital Signs		X	X			
Medications Summary	X	X			X	
Fluid Intake and Urine Output	X	X			X	
Surgical Data with Operative Summary Report and CPB Record		X				
Post Operation Notes		X			X	
Review of AE's, renal replacement therapies	X	X			X	X
Aortix Deployment		X				
Fluoro Image of pump		X				
Required labs (see details App. B)	X		X		X	X
Re-hospitalization, LOS data						X

\*Document the most recent EF recorded post-surgery (if available). Acceptable if it is out of the window.

Category	Schedule of Data Collection for Patients with Aortix Removed in a Separate Procedure Post-Surgery (Aortix Arm)						
	Pre-Surgery Period (Baseline Monitoring)	Surgery and Aortix Implant	Aortix Retrieval Post-Surgery	Post-Surgery Monitoring (in Hospital)			Study Exit (Day 30 Post-Surgery)
	Current hospitalization once	Once	Once	24 Hours Post-Surgery (± 1 hour)	At 72 hours Post-Surgery (± 4 hours)	Daily starting at 24 Hours Post-Surgery until Hospital Discharge or Day 7, if still hospitalized (± 6 hours)	Study Exit Visit ± 3 Days
Informed Consent	X						
Anatomy Screening	X						
Med History and Physical Exam	X						
Collect Admission H&P	X						
Weight and Ejection Fraction (EF)	X				X*		
Vital Signs		X		X			
Medications Summary	X	X				X	
Fluid Intake and Urine Output	X	X	X			X	
Surgical Data with Operative Summary Report and CPB Record		X	X				
Post-Operation Notes		X	X			X	
Review of AE's, renal replacement therapies	X	X	X			X	X
Aortix Retrieval			X				
Fluoro Image of pump		X	X				
Required labs (See details App. B)	X			X		X	X
Re-hospitalization, LOS data							X

\*Document the most recent EF recorded post-surgery (if available). Out of window measurement acceptable (not a deviation) for EF.

Category	Schedule of Data Collection for Patients Who Do Not Receive the Aortix Pump (Non-Aortix Arm)					
	Pre-Surgery Period (Baseline Monitoring)	Surgery	Post-Surgery Monitoring			Study Exit (Day 30 Post-Surgery)
	Current hospitalization once	Once	24 Hours Post-Surgery (± 1 hour)	At 72 hours Post-Surgery (± 4 hours)	Daily starting at 24 Hours Post-Surgery until Hospital Discharge or Day 7, if still hospitalized (± 6 hours)	Study Exit Visit ± 3 Days
Informed Consent	X					
Anatomy Screening**	X					
Med History and Physical Exam	X					
Collect Admission H&P	X					
Weight and Ejection Fraction (EF)	X			X*		
Vital Signs		X	X			
Medications Summary	X	X			X	
Fluid Intake and Urine Output	X	X			X	
Surgical Data with Operative Summary Report and CPB Record		X				
Post Operation Notes		X			X	
Review of AE's, renal replacement therapies	X	X			X	X
Required labs (See details App. B)	X				X	X
Re-hospitalization, LOS data						X

\*Document the most recent EF recorded post-surgery (if available). Acceptable if it is out of the window.

\*\*If patient consents to and undergoes anatomical screening

